### **Statistical Analysis**

All statistical summaries and 2-sample t-tests were performed using the Data Desk® version 6.3. Comparison of these changes between treatment groups are also shown as 95% confidence intervals (CI). The chi-square test or Fisher's exact test was applied to analyze baseline demographics, improvement with GRA treatment responders, and the proportion of patients with a reduction from baseline of 30% or greater in their pain intensity score between treatment groups.

### **Safety Evaluation**

Patients will be assessed at office visits and by continuous availability by phone for adverse events. Adverse effects may include rhinitis, headache, rash, pruritus, injection site reaction, infections, tuberculosis, cancer, and demyelinating diseases.

#### **Stopping Criteria for Adverse Events**

#### **Serious infections:**

These include TB and infections caused by viruses, fungi, or bacteria. Symptoms related to TB include cough, low-grade fever, weight loss, or loss of body fat and muscle.

### Allergic reactions:

Signs of a serious allergic reaction include skin rash, a swollen face, or trouble breathing.

### **Nervous system problems:**

Signs and symptoms include numbness or tingling, problems with your vision, weakness in your arms or legs, and dizziness.

# **Blood problems**:

Symptoms include a fever that does not go away, bruising or bleeding very easily, or looking very pale.

# New heart failure or worsening of heart failure you already have:

Symptoms include shortness of breath or swelling of your ankles or feet, or sudden weight gain.

# Immune reactions including a lupus-like syndrome:

Symptoms include chest discomfort or pain that does not go away, shortness of breath, joint pain, or rash on your cheeks or arms that gets worse in the sun.

Statistical Analysis Plan

Pilot Study Evaluating the Efficacy of Certolizumab Pegol for Interstitial

Sample size

Previous IC/BPS studies demonstrated an approximate 20% placebo response rate [29]. Monotherapy response rate of certolizumab pegol in rheumatoid arthritis was 45% [21]. To achieve an 80% power using 2:1 randomization and a 2-sided $p = .05$ a minimum of 39 subjects was required. The sample size was increased by 3 subjects to account for potential participant withdrawals.

Randomization

Eligible participants were computer randomized and received either subcutaneous certolizumab pegol 400gm or placebo (sterile saline) in a 2:1 ratio at weeks 0, 2, 4, and 8. The study drug and placebo were provided in ready to use syringes that were identical other than the blinded ID number on the side of the syringe.

Statistical analysis

Any patient who withdrew from the study, for whatever reason, was classified as a non-responder.

All statistical summaries and 2-sample t-tests were performed using the Data Desk® version 6.3. Comparison of these changes between treatment groups are also shown as 95% confidence intervals (CI). The chi-square test or Fisher's exact test was applied to analyze baseline demographics, improvement with GRA treatment responders, and the proportion of patients with a reduction from baseline of 30% or greater in their pain intensity score between treatment groups.

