The FDA asked for more outcome measures so ICPI and numeric rating scale for pain and urgency was added. They asked for monitoring of patient with outcome data to week 18. We also agreed to change the potential total number of patients from 44 to 42 as this would maintain the 2:1 study medication ratio.

Condition	Intervention	Phase
Cystitis, Interstitial	Biological: Certolizumab pegol (Cimzia)	Phase III
Bladder Pain Syndrome	Other: Placebo	

Study Type: Interventional

Study Design: Randomized, Double-Blind, Placebo Controlled Treatment, Efficacy Study

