### **Secondary Outcome Measures**

Improvement in GRA at week 4, 10, and 18

Improvement in the Interstitial Cystitis Symptom Index (ICSI) Interstitial Cystitis Problem Index (ICPI) from baseline to week 2, 4, 10, and 18

11-point numeric pain and urgency scale at baseline, week 2, 4, 10, and 18

Midstream first void urine specimen level of TNF $\alpha$  normalized to urinary creatinine, at week 2,

4, 10, and 18 compared to baseline levels

Adverse events from time of Screening through the last clinic and phone call visit

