# **Estimated enrollment** 42 patients

After subjective evaluation of efficacy and safety in the initial 30 patients, the total study sample size will be 42 study patients.

Previous IC/BPS studies demonstrated an approximate 20% placebo response rate. Monotherapy response rate of certolizumab pegol in rheumatoid arthritis was 45%. To achieve an 80% power using 2:1 randomization and a 2-sided p = .05 a minimum of 39 subjects was required. The sample size was increased by 3 subjects to account for potential participant withdrawals.

Arms	Assigned Intervention					
Group 1: Experimental	Biological: Certolizumab pegol (Cimzia) 400 mg pre-filled syringe loading dose given subcutaneously at week 0, 2, and 4 followed by a maintenance dose at week 8					
Group 2: Placebo Comparator	Placebo: given subcutaneously at week 0, 2, 4, and week 8					

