### **Inclusion Criteria**:

- 1. A diagnosis of IC/BPS defined based on AUA guidelines as the following: an unpleasant sensation (pain, pressure, discomfort) perceived to be related to the urinary bladder, associated with lower urinary tract symptoms of more than 6 months duration, in the absence of infection or identifiable causes, documented history or patient reported.
- 2. Only those patients with moderate to severe IC/BPS will be included in the study.
- 3. Able to provide informed consent to participate in the study and comply with study requirements
- 4. Able to provide written authorization for use and release of health and research study information
- 5. Written documentation of being provided California's Experimental Subject's Bill of Rights
- 6. Females ≥18 and ≤ 65 years of age previously diagnosed with interstitial cystitis/ bladder pain syndrome (IC/BPS) for a duration of greater than 6 months
- 7. Female patients of child-bearing potential must have a negative serum pregnancy test at Screening and use birth control while in the study.
- 8. O'Leary-Sant Interstitial Cystitis Symptom and Problem Indexes (OSPI) score ≥ 18
- 9. No history of any cancer.
- 10. No bacterial cystitis in previous 1 month
- 11. No active herpes in previous 3 months
- 12. Never treated with cyclophosphamide
- 13. No neurogenic bladder dysfunction (due to a spinal cord injury, stroke, Parkinson's disease, multiple sclerosis, spina bifida or diabetic cystopathy)
- 14. Absence of bladder, ureteral or urethral calculi for previous 3 months

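### The continuous secondary outcomes are to be compared by unadjusted t-tests, although a baseline is already planned for each; ANCOVA would probably narrow the intervals at small cost

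*SAP*

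**What the plan says.** The Statistical Analysis section of the protocol and the SAP use the same wording. "All statistical summaries and 2-sample t-tests were performed using the Data Desk" package, and "Comparison of these changes between treatment groups are also shown as 95% confidence intervals (CI"). Chi-square or Fisher tests are named for baseline demographics, GRA responders and the 30% pain-reduction proportion. Neither document mentions a covariate, a regression or ANCOVA, and neither defines which changes are meant.

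The protocol's Secondary Outcome Measures section fills part of that gap:

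- ICSI and ICPI are framed as change: "Improvement in the Interstitial Cystitis Symptom Index (ICSI) Interstitial Cystitis Problem Index (ICPI) from baseline to week 2, 4, 10, and 18".
- So is urinary TNFα over creatinine, at week 2 and weeks "4, 10, and 18 compared to baseline levels".
- Pain and urgency are listed by time point only: "11-point numeric pain and urgency scale at baseline, week 2, 4, 10, and 18". Their t-test could be on change or on follow-up scores.

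A baseline is planned for all five. The Trial Schedule marks the pain and urgency scales at week 0. Study Design plans a baseline urine sample and a baseline OSPI, which contains ICSI and ICPI. The schedule marks the OSPI at screening and at the reevaluation visit (week -1), with no ICSI or ICPI mark at week 0.

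**The concern.** In a randomised comparison, adjusting a continuous outcome for its own baseline usually gives a more precise treatment difference than comparing raw changes or raw follow-up scores. Subtracting the baseline in full amounts to fixing the slope of follow-up on baseline at 1. Ignoring the baseline fixes it at 0. ANCOVA estimates the slope from the data.

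Precision is scarce here: 42 patients at 2:1 leave 28 on active treatment and 14 on placebo. Some of these outcomes were a regulatory request: "The FDA asked for more outcome measures so ICPI and numeric rating scale for pain and urgency was added". What is at stake is the width of the secondary-outcome confidence intervals. The primary GRA asks about change since the start of the trial and has no baseline value to adjust for. The 30% pain-reduction analysis is not questioned.

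**Working it through.** **Plan's own figure.** There is none to reproduce: the documents give no SD, correlation or power for any continuous outcome. The 39 and 42 patients belong to the binary primary endpoint and serve here only as sample sizes. N = 39 is the case in which the planned allowance for losses is used up: "The sample size was increased by 3 subjects to account for potential participant withdrawals".

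**Assumed inputs.** r is the correlation of baseline with follow-up (0.3 to 0.7). k is follow-up SD divided by baseline SD (0.75 to 1.5). At first, both arms share the same r and k.

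**Formulas, in units of baseline variance.**

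- Change score: 1 + k² − 2rk.
- ANCOVA residual: k²(1 − r²).
- Difference: (1 − rk)², which is never negative.
- Expected cost of estimating the slope: a factor 1 + 1/(N − 4), which is 1 + 1/38 = 1.026 at N = 42 and 1 + 1/35 = 1.029 at N = 39.

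Example: with r = 0.5 and k = 1, 0.75/1.00 × 1.026 = 0.770, a 23% cut.

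**Change in variance, ANCOVA against change scores, N = 42.**

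| k | r = 0.3 | r = 0.5 | r = 0.7 |
|---|---|---|---|
| 0.75 | −53% | −47% | −43% |
| 1 | −33% | −23% | −13% |
| 1.25 | −19% | −8% | +1% |
| 1.5 | −11% | −1% | +2% |

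The largest loss inside the range is not at the corner (2.4%) but where rk = 1, for example r = 0.7 and k = 1.43. There the two residual variances are equal and only the slope cost remains: 2.6%, or 2.9% at N = 39. The other N = 39 figures lie within 0.3 percentage points of the table. Simulation of 28 against 14 patients agrees: variance ratios 0.470 (r = 0.3, k = 0.75), 0.771 (r = 0.5, k = 1) and 1.027 (r = 0.7, k = 1.43).

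**Interval width at k = 1, N = 42.** The 95% half-widths in baseline SDs, change score then ANCOVA, are 0.783 and 0.640 (r = 0.3), 0.662 and 0.581 (r = 0.5), and 0.512 and 0.479 (r = 0.7). The intervals are 18%, 12% and 7% narrower.

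**If pain and urgency are tested on follow-up scores.** The gain is 1 − (1 − r²) × 39/38 = 7%, 23% and 48% for r = 0.3, 0.5 and 0.7, whatever k is.

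**ICSI and ICPI under the entry rule.** Entry requires "Symptom and Problem Indexes (OSPI) score ≥ 18", which trims the low end of the baseline and pushes k above 1. The model takes a normal baseline with equal SDs and correlation 0.3, 0.5 or 0.7 before trimming, and treats the rule as a cut on the score itself. The share removed is assumed.

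| Share cut | Baseline variance left | k | Gain |
|---|---|---|---|
| Lowest 20% | 0.583 | 1.28, 1.24, 1.17 | 22%, 14%, 7% |
| Lowest 50% | 0.363 | 1.61, 1.52, 1.38 | 14%, 8%, 4% |

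**If the arms differ.** Take active at r = 0.3, k = 0.75 (slope 0.225) and placebo at r = 0.7, k = 1.5 (slope 1.05).

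- The pooled slope leans towards the larger arm: (27 × 0.225 + 13 × 1.05)/40 = 0.493.
- Change-score variance: 1.1125/28 + 1.15/14 = 0.1219.
- Variance with slope 0.493: 0.5838/28 + 1.4577/14 = 0.1250, a ratio of 1.025 before the cost of estimating the slope.
- Simulation with that cost included (300,000 trials) gives 1.048.

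A more extreme case outside the assumed ranges, with slopes 0.6 (active) and 1.2 (placebo) and residual variance 0.5 in both arms, gives about 1.10.

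**The case against.** The strongest reply is that nothing in the plan is wrong. A t-test with an interval on change is valid, and it answers directly the improvement from baseline that the protocol names for ICSI and ICPI. Every magnitude above rests on assumed inputs, and the sign reverses in about 9% of the assumed grid. Both documents also describe the analysis in the past tense, so it may already be done. All of this stands. It makes the point an optional gain in precision rather than a correction.

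Two stronger readings are tempting, and neither is supported.

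- A reader might infer that ANCOVA can never cost more than 2.6% of variance. That holds only with a common slope and SD ratio in both arms. Under 2:1 allocation the pooled slope follows the larger arm, whereas the most precise slope would give more weight to the smaller one. Losses of about 5% and 10% can then be constructed.
- A reader might take the 53% cut as the likely gain. It needs a follow-up SD below the baseline SD, whereas the entry threshold points the other way for ICSI and ICPI. Entry is also limited to moderate or severe disease, which may narrow baseline pain and urgency too.

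The objection does not remove the asymmetry. Most plausible inputs give a gain, the losses found are small, and the baseline is to be collected anyway.

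**Conclusion.** The point holds as one to consider. The plan leaves probable precision unused in its continuous secondary outcomes. With equal SDs the gain against change scores is about 33%, 23% or 13% of variance for r = 0.3, 0.5 or 0.7 at N = 42. For ICSI and ICPI about 4% to 22% is the better guide. Over the whole assumed range with arms alike, the result runs from a 53% cut to a 2.6% loss (2.9% at N = 39). With unlike arms the loss can be somewhat larger, so 2.6% is not an absolute cap. All of these figures rest on assumed correlations, SD ratios and trimming shares.

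The finding should not be read as saying that the t-tests are biased or invalid, or that a power statement fails. Randomisation protects the unadjusted comparison, and the documents make no power claim for these outcomes.

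**What to change.** Replace the t-test sentence in both documents with wording to this effect:

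> ICSI, ICPI, pain, urgency and urinary TNFα/creatinine are each analysed at weeks 2, 4, 10 and 18 by ANCOVA, with treatment arm and the baseline value of the same outcome in the model. Baseline is the last OSPI before randomisation for ICSI and ICPI, and the week 0 value for the others. The adjusted mean difference and its 95% confidence interval are reported.

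Use the same patients that a change-score t-test would use; how missing continuous data are handled is a separate question. The wording also settles which outcomes and which baseline visit are meant.

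If the analysis has already been done, keep the t-test and report the ANCOVA beside it, labelled post hoc.

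The cost is a change of wording and one degree of freedom, with a small possible loss of precision when the true slope is near 1 or differs between arms. No new data or patients are needed.

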### **Primary Outcome Measures**

The primary endpoint is improvement in global response assessment (GRA) at week 2

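### The primary test is left as chi-square or Fisher's exact, with no selection rule or statement on continuity correction; at 28:14 this can change significance and lets the true size reach 6.3%

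*SAP*

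**What the plan says.** The protocol (Primary Outcome Measures) names a single primary comparison: "The primary endpoint is improvement in global response assessment (GRA) at week 2". The SAP (Statistical analysis) then gives the method: "The chi-square test or Fisher's exact test was applied to analyze baseline demographics, improvement with GRA treatment responders". The protocol (Statistical Analysis) has the same sentence, beginning "The chi-square test or Fisher's exact test was applied to analyze baseline demographics". It covers baseline demographics, GRA responders and the 30% pain-reduction responders alike, so the primary endpoint gets no rule of its own.

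Neither document states which test is primary, gives a criterion for choosing (such as an expected-count threshold), or says whether a continuity correction applies.

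The error level and planning inputs are in the protocol (Estimated enrollment) and the SAP (Sample size): "To achieve an 80% power using 2:1 randomization and a 2-sided p = .05", with "Previous IC/BPS studies demonstrated an approximate 20% placebo response rate" and 45% assumed on active treatment. The total is 39, raised to 42. The SAP also counts every withdrawal as a non-responder.

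**The concern.** In a large trial the two tests give nearly the same p-value and the wording would be harmless. With 14 patients on placebo they do not. The uncorrected chi-square relies on a large-sample approximation and can exceed its nominal level. Fisher's test is exact but conservative. A Yates-corrected chi-square is more conservative still.

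So the plan as written does not fix the type I error or the power of its one primary test. A result between the two rejection regions could be reported as positive or negative, and both reports would comply with the plan.

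**Working it through.** **Inputs.** 42 patients at 2:1 gives 28 active and 14 placebo. Because withdrawals count as non-responders, these denominators stay fixed. The level is 0.05 two-sided; the planning rates are 20% and 45%.

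**The plan's own figure.** With placebo rate 0.20, active rate 0.45 and allocation 2:1, the pooled rate is (0.20 + 2 × 0.45)/3 = 0.367. The placebo group size is

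[1.96 × √(0.367 × 0.633 × 1.5) + 0.842 × √(0.20 × 0.80 + 0.45 × 0.55/2)]² / 0.25² ≈ 41.2,

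or about 123.7 in total, 126 after rounding up. The stated 39 is not reproduced. That is a separate and larger issue; it matters here only because power is already low.

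**Method.** List all 29 × 15 = 435 possible outcomes (a responders of 28, b of 14). Mark whether each test gives p ≤ 0.05, and sum

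Bin(a; 28, p₁) × Bin(b; 14, p₀)

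over the rejected outcomes. Setting p₁ = p₀ gives the true size; the maximum is taken over common rates from 0.001 to 0.999. Setting p₁ = 0.45 and p₀ = 0.20 gives power.

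| Test at 28:14 | Size at 20% common rate | Maximum size | Power, 45% vs 20% |
|---|---|---|---|
| Chi-square, uncorrected | 4.6% | 6.3% (at 50%) | 37.9% |
| Chi-square, Yates | 1.6% | 2.2% | 22.1% |
| Fisher's exact | 2.9% | 3.9% | 33.2% |
| Fisher if any expected count is below 5, otherwise uncorrected chi-square | 2.9% | 6.3% | 36.4% |
| Boschloo's exact | not needed | 5.0% | 37.2% |

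The uncorrected chi-square has size 5.1% at a common rate of 25%, 5.4% at 30% and 5.9% at 40%. It is above 5% for common rates of about 23% to 77%. At the stated minimum of 39 patients (26:13) it is 5.1% at 20%, with a maximum of 5.4%.

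**How often the choice decides the result.** Uncorrected chi-square is significant and Fisher is not in:
- 4.7% of trials under 45% vs 20% (37.9% − 33.2%), about 1 in 21;
- 1.7% of trials under a 20% null, about 1 in 57;
- at most 2.9% of trials under any null rate.

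None of the 435 outcomes is significant by Fisher but not by uncorrected chi-square. Under the planned effect, 4.74/37.94 = 12.5% of chi-square positives are not Fisher positives.

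Two such outcomes:
- 15/28 vs 3/14: χ² = 42 × (15 × 11 − 3 × 13)² / (28 × 14 × 18 × 24) = 3.94, p = 0.047; Fisher p = 0.057.
- 10/28 vs 1/14: chi-square p = 0.047; Fisher p = 0.067.

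**Would the usual convention settle it?** Under the planned rates the expected placebo responder count is (28 × 0.45 + 14 × 0.20) × 14/42 = 15.4/3 = 5.13, almost on the customary limit of 5. In 39% of such trials the smallest expected count is below 5, so the convention would pick Fisher in those and chi-square in the rest. Of the two examples, the first (smallest expected count 18 × 14/42 = 6.0) would go to chi-square and the second (11 × 14/42 = 3.67) to Fisher.

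**The case against.** The strongest reply is that at the plan's own 20% rate nothing is inflated: the uncorrected chi-square has size 4.6%. That stands, and a reader who infers that chi-square breaks the 5% level in this trial goes too far. The excess needs a common rate above about 23% at 28:14, and it needs the uncorrected test; with Yates' correction the size never passes 2.2%. Still, the 20% is described as approximate, and the protocol's background section attributes the failure of the investigator's previous trial against placebo to a large placebo effect. The behavioural-advice period before randomisation is meant to reduce that effect, but does not guarantee a rate below 23%.

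Second, a flat claim that the tests disagree in 1 trial in 20 would mislead. It holds under 45% vs 20%. Under a 20% null the figure is 1.7%.

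Third, an expected-count rule depends only on the total number of responders, so it can be applied without seeing results by arm and is not cherry-picking. At a 20% null it selects Fisher in 98.7% of trials and has size 2.9%. That also stands, but neither document adopts the rule, and its size still reaches 6.3% at higher common rates.

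Fourth, the gain from Boschloo over Fisher is only about 4 points of power, small beside the sample-size problem. This bears on priority, not on whether one test should be named.

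**Conclusion.** The point holds in this conditional form. The primary test and any continuity correction are not fixed. The wording allows a maximum true size anywhere from 2.2% to 6.3% and power from 22.1% to 37.9% for the planned effect. The possible excess over the stated level is modest, at most 1.3 points (6.3 − 5.0). The more practical risk is that an ordinary borderline result changes status with the test. Between Fisher and uncorrected chi-square, the open choice can only add significant results.

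A reader might infer that the test was chosen after the data were seen. The documents do not support that. They are written in the past tense but do not say when or how the choice was made; they show an ambiguity and nothing more.

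The figures assume an exact 28:14 split, independent binary responses and rejection at p ≤ 0.05. Priority: should be changed, ranking below the sample-size figure that its own inputs do not reproduce.

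**What to change.** In the protocol's Statistical Analysis section and the SAP's Statistical analysis section, name one test for GRA responders at week 2 and remove chi-square for that endpoint.

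- **Preferred:** Boschloo's unconditional exact test, two-sided at 0.05. Its size is at most 5.0%, its power is 37.2%, and it rejects every outcome that Fisher rejects.
- **Simpler alternative:** Fisher's exact test, at a cost of 37.2 − 33.2 = 4.0 points of power.

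The cost is one sentence in each document, with no change to trial conduct. Boschloo's test may need software other than the package named; the documents tie that package to summaries and t-tests and do not say what it offers for exact tests.

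If the data are already unblinded, the sponsor should instead report which test was used, when it was chosen, and both p-values, stating whether the chi-square was continuity-corrected.
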